10.9 VISIT MODIFICATION IN EXCEPTIONAL CIRCUMSTANCES

In the event of force majeure or other disruptive circumstances (e.g. pandemic), in case site visits are temporarily not possible for individual patients, to ensure trial continuity the following measures may be implemented at a site if possible per local requirements in the participating country. Implemented measures should be documented and needed approvals should be obtained upon (see [Section 6.1](#) and ISF for details).

Table 10.9: 1 Modifications to visit standard procedures in exceptional circumstances

| STANDARD PROCEDURE | POSSIBLE MODIFICATION |
|--|---|
| 
Face-to-face patient visit performed by an adequate site staff under the responsibility of a physician on site.
 | 
 • for Visit 3 Visit 4 and Visit 5: no possibility to postpone the visits more than initial time window defined by CTP except in case of agreement with sponsor and after discussion and evaluation of individual patient benefit risk. • for the following visits, visits may be converted to home visits, or combined home and remote visits. If physical exam, vital signs, height, weight cannot be conducted at least every 16 weeks, the individual patient treatment needs to be interrupted upon discussion with the sponsor. Medical decision has to be documented in patient’s source notes. 
Home visit performed (with portable stadiometer, tape, scale, ECG machine, pulseoximeter to measure SpO₂) by the (sub)investigator or delegated and trained personnel to complete at least:
 
 • Physical examination and vital signs • Height sitting and standing • Leg length • Weight • ECG • SpO₂ • Safety Lab using central lab kits if possible (otherwise use local lab facility, see below for instructions) • Questionnaires administered as an interview using printed questionnaires (if not done by separate call, see below for instructions) • Transfer imaging CDs of bone MRI/x-ray and panoramic x-ray to site (when needed) • Collect medication for IMP compliance • Assessments listed under “Investigator Call,” if not done by separate call 
Investigator Call: the following assessments could be completed by the (sub)investigator via phone or telemedicine, if not done during the home visit:
 |

| STANDARD PROCEDURE | POSSIBLE MODIFICATION |
|--|--|
| | 
[REDACTED]
 
 • ILD exacerbations • Hospitalizations • AEs, SAEs, AESI • Trial medication and concomitant medications • Questionnaires administered as an interview using printed questionnaires • Pregnancy status and pregnancy diary completion check 
The following assessments cannot be made outside the investigational site:
 
 • FVC • 6MWT • PK sampling 
[REDACTED]
 
PK sampling will be conducted at the next scheduled visit at the site, as far as the study medication was regularly taken in the 10 days before PK sampling, and intake in the 3 days before PK sampling was documented in the PK diary card.
 
FVC, 6MWT and [REDACTED] will be missed if the scheduled visit is converted to home visit, or combined home and remote visit.
 |
| 
Safety lab testing conducted at site using central lab kits
 
 • Haematology • Biochemistry • Electrolytes • Coagulation • Urinalysis • | 
Under treatment with nintedanib, regular safety lab including liver enzyme monitoring is required and needs to be ensured by the investigational site. If blood and urine sampling for safety lab testing at the trial site is not possible
 
 • samples could be collected at a local lab / local doctor using central lab kits and sent to central lab for analyses. If this is not possible, • safety lab analyses can be performed at a local lab. The results of the lab tests must be transferred to the investigator who ensures medical review and documents any clinically relevant safety issue as an adverse event. 
Safety lab tests including liver function tests should be conducted at the planned timepoint defined by CTP. If safety lab tests cannot be conducted at least every 16 weeks, the individual patient treatment needs to be interrupted upon discussion with the sponsor. Medical decision has to be documented in patient's source notes.
 |
| 
Pregnancy test on blood conducted at site using central lab kits – female subjects only
 | 
If blood sampling for pregnancy test at the trial site is not possible
 
 • Urine dipstick pregnancy tests will be used • Testing must occur every 4-6 weeks and results documented in the pregnancy test diary card. • The results of the pregnancy tests must be transferred to the investigator who ensures medical review, documents any test results as needed, and reports any positive results as defined by CTP. |

| STANDARD PROCEDURE | POSSIBLE MODIFICATION |
|--|---|
| | 
If pregnancy tests cannot be conducted every 4-6 weeks, the individual patient treatment needs to be interrupted upon discussion with the sponsor. Medical decision has to be documented in patient's source notes.
 |
| 
Follow-up monitoring of bone and teeth conducted at site/external facilities
 
 • Bone MRI/x-ray • Dental examination • Dental panoramic x-ray | 
If regular follow-up monitoring of bone and teeth at site is not possible
 
 • Bone MRI/x-ray, dental examination and dental panoramic x-ray can be performed at a local radiologist/ local dentist • The results (images and dental examination report) must be transferred to the investigator, who will send images to central reading, ensure medical review, and document any clinically relevant safety issue as an adverse event. 
Follow-up monitoring of bone and teeth should be conducted at the planned timepoint defined by CTP. If bone MRI/x-ray and/or dental examination cannot be conducted at least every 16 weeks (first year)/28 weeks (second year), and/or if dental panoramic x-ray cannot be conducted at least every 28 weeks (first year)/1 year (thereafter), the individual patient treatment needs to be interrupted upon discussion with the sponsor. Medical decision has to be documented in patient's source notes.
 |
| 
Dispensation of study medication on site
 | 
If study medication cannot be dispensed during a regular visit at the site
 
 • Direct to patient IMP shipment from Site can be requested • The patient's parent(s)/legal guardian (or the patient if applicable) must consent to provide contact details for shipping purposes • The patient's parent(s)/legal guardian (or the patient if applicable) should retain all unused IMP and packaging, and return it to the site as soon as possible (e.g. via Investigator in case of home visit, or when they are able to attend a visit at the site, or by other means defined with the site staff and approved by the sponsor). |

The investigator will take the totality of information related to each single patient and the local COVID-19 situation into consideration when performing the individual benefit-risk assessment on a case-by-case basis. Considering all aspects, the investigator will decide upon each patient's (continued) participation in the trial. The sponsor, where required, will support the investigator in their decision making. It is acknowledged that the investigator may decide to implement protocol deviations where this protects the safety, wellbeing and/or is in the best interest of the patient.

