| Statistical methods | 
Descriptive statistics will be provided for PK and safety endpoints. Analysis of secondary endpoints will be descriptive in nature using a mixed model with repeated measurements (MMRM) for continuous endpoints. Time-to-event endpoints will be displayed descriptively using the Kaplan-Meier method. Categorical endpoints, safety and tolerability will be displayed descriptively in frequency tables.
 |

FLOW CHART

| Trial Periods | Screening | | Treatment* | | | | | | | | | | | | | | | Follow-up |
|--|------------------------------------|---------------------|-------------------|-------|-------|-------|-----------|--------|-------------------|-----------|--------|-----------|--------|-----------|------------------|-----------|-------|---------------------|
| | | | Randomised Part A | | | | | | Open label Part B | | | | | | | | | |
| Visit | | 1 | 2 | 3 | 4 | 5 | 5a | 6 | 7 | 7a | 8 | 8a | 9 | 9a | X | Xa | EoT** | EoTrial*** |
| Weeks**** | | -4 | 0 | 2 | 6 | 12 | as needed | 24 | 26 | as needed | 36 | as needed | 52 | as needed | 52 plus Q12w | as needed | | |
| Days**** | Before or at the latest at Visit 1 | ≤28d before Visit 2 | D 1**** none | 15 ±3 | 43 ±3 | 85 ±3 | na | 169 ±3 | 183 ±3 | na | 253 ±7 | na | 365 ±7 | na | 365 plus Q84d ±7 | na | | EoT plus 28 days +3 |
| Informed consent and assent ¹ | X | | | | | | | | | | | | | | | | | |
| HRCT sent to central review ² | X | | | | | | | | | | | | | | | | | |
| Biopsy sent to central review (if required) ² | X | | | | | | | | | | | | | | | | | |
| Demographics | X | | | | | | | | | | | | | | | | | |
| Medical history | X | | | | | | | | | | | | | | | | | |
| Physical examination, Vital signs ³ | X | X | X | X | X | X | | X | X | | X | | X | | X | | X | X |
| Height (standing and sitting) ⁴ | X | X | X | | | X | | X | | | X | | X | | X | | X | (X) |
| Leg length | | | X | | | X | | X | | | X | | X | | X /Q24w | | X | |

| Trial Periods | Screening | | Treatment* | | | | | | | | | | | | | | | Follow-up |
|---|------------------------------------|---------------------|-------------------|----------|----------|----------|-----------|-----------|-------------------|-----------|-----------|-----------|-----------|-----------|------------------|-----------|-------|---------------------|
| | | | Randomised Part A | | | | | | Open label Part B | | | | | | | | | |
| Visit | | 1 | 2 | 3 | 4 | 5 | 5a | 6 | 7 | 7a | 8 | 8a | 9 | 9a | X | Xa | EoT** | EoTrial*** |

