Cases of drug-induced liver injury (DILI) have been observed with nintedanib treatment in adults. The majority of hepatic events occur within the first three months of treatment, therefore hepatic transaminase and bilirubin levels should be investigated upon the initiation

of treatment with nintedanib, at regular intervals during the first three months of treatment and periodically thereafter or as clinically indicated.

Considering that VEGFR inhibition might potentially be associated with an increased risk of bleeding, patients at known risk for bleeding or who required fibrinolysis, full-dose therapeutic anticoagulation, or high dose antiplatelet therapy have been excluded from participation in the nintedanib trials, and initiation of any of these therapies during the course of the trials required discontinuation of the study medication.

For a more detailed description of the nintedanib profile, please refer to the current IB Nintedanib in Idiopathic Pulmonary Fibrosis, Systemic Sclerosis and Progressive Fibrosing Interstitial Lung Disease [[c01783972-16](#)].

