5.4.4.1 Time-to-event analyses for liver enzyme elevations

- Time to liver enzyme and bilirubin elevation (ALT and/or AST $\geq 3 \times \text{ULN}$ and bilirubin $\geq 2 \times \text{ULN}$)
- Time to liver enzyme elevation (ALT and/or AST $\geq 5 \times \text{ULN}$)
- Time to liver enzyme elevation (ALT and/or AST $\geq 3 \times \text{ULN}$)

Time to first occurrence of the above described liver enzyme elevations [days] will be analyzed as

$$\text{Date of event/censoring} - \text{Date of first treatment intake} + 1 \text{ day.}$$

Patients with no such event occurred during the respective period will be censored according to the mechanism for censoring as described in [Table 5.4.4.1: 1](#).

Table 5.4.4.1: 1 Censoring rules for time to first occurrence of liver enzyme elevations

Rule	Situation	Outcome	Date of event/censoring
1	Patient had a documented event during treatment or REP ^[1] of respective period	Event	Earliest date of event
2	Patient had no documented event during treatment or REP ^[1] of respective period.	Censored	Earliest date of 
 • end date of REP of respective period, • date of last contact when patient was known to be alive and event free, • date of death.

^[1] See [Sec. 6.1](#) for definition of Residual Effect Period (REP)

These times to onset of first event will also be summarized in categories:

- Double-blind period:
 - ≤2 weeks (14 days)
 - >2 to ≤6 weeks (42 days)
 - >6 to ≤12 weeks (84 days)
 - >12 to ≤18 weeks (126 days)
 - >18 to ≤24 weeks (168 days)
 - >24 weeks (168 days)
 - Censored

- Nintedanib exposure period, over the whole trial:
 - ≤2 weeks (14 days)
 - >2 to ≤6 weeks (42 days)
 - >6 to ≤12 weeks (84 days)
 - >12 to ≤24 weeks (168 days)
 - >24 to ≤36 weeks (252 days)
 - >36 to ≤52 weeks (364 days)
 - >52 to ≤64 weeks (448 days)
 - >64 to ≤76 weeks (532 days)
 - >76 weeks (532 days)
 - Censored

Further categories might be defined if needed.

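### In Appendix 10.9 the 16-week limit on missed liver tests outlasts the three-month hepatic risk period for children who start nintedanib at Visit 6, and the SAP censors liver endpoints without reference to the last liver test

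*Protocol*

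**What the plan says.** **Timing of risk.** Protocol section 1.2 states: "The majority of hepatic events occur within the first three months of treatment". It asks for transaminases and bilirubin to be checked at the start of treatment and regularly during those months.

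**Visit row of Table 10.9: 1 (Appendix 10.9, exceptional circumstances only).** The rule reads "for Visit 3 Visit 4 and Visit 5: no possibility to postpone the visits more than initial time window defined by CTP", followed by the exception "except in case of agreement with sponsor and after discussion and evaluation of individual patient benefit risk". From Visit 6 onward, "for the following visits, visits may be converted to home visits, or combined home and remote visits". The minimum content of a home visit includes the safety laboratory.

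**Laboratory row of the same table.** The site must ensure liver monitoring under nintedanib. Samples may be taken locally with central kits or, failing that, analysed locally. The default is "Safety lab tests including liver function tests should be conducted at the planned timepoint defined by CTP". The limit with a consequence is "If safety lab tests cannot be conducted at least every 16 weeks, the individual patient treatment needs to be interrupted". This row draws no distinction between visits.

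**Start of nintedanib.** Placebo-randomised children switch to open-label nintedanib at Visit 6 (section 3.1). Section 6.2.2 has that visit's laboratory blood drawn before the dose.

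**Analysis.** SAP section 5.4.4 analyses liver elevations for the double-blind period, the nintedanib exposure period and the whole trial. Under SAP Table 5.4.4.1: 1, a child without a documented event is censored at the earliest of the end of the residual effect period (REP), the "date of last contact when patient was known to be alive and event free", and death.

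**The concern.** The stated hepatic risk follows the first nintedanib dose, while the stricter visit rule follows randomisation. The two coincide for children randomised to nintedanib. For placebo-randomised children, weeks 2 to 12 are spent on placebo, and the first three months on drug fall under the more flexible wording for later visits. The limit that forces interruption is also longer than the risk period, and nothing restarts it at the first active dose.

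Two things are at stake. One is safety monitoring, in exceptional circumstances, in about a third of the trial. The other is the reading of the liver results: an enzyme elevation without symptoms is seen only if blood is tested, yet the SAP's censoring dates do not depend on testing.

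**Working it through.** The plan gives no figure for this point, so the check is day arithmetic on its own schedule.

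**Inputs.** Flow Chart visit days are 15, 43, 85, 169, 183 and 253 for Visits 3 to 8. They reproduce as 1 + 7 × week for weeks 2, 6, 12, 24, 26 and 36. The synopsis gives about 20 children on nintedanib and 10 on placebo. The laboratory limit is 16 × 7 = 112 days. Three months is taken as 84 days (12 weeks) to 91 days (365.25/4).

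**Scheduled on-drug liver tests in the first 12 weeks of nintedanib**

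| Group | First nintedanib dose | On-drug tests | Stricter visit rule applies |
|---|---|---|---|
| Randomised to nintedanib | day 1 | weeks 2, 6, 12 | yes, unless the sponsor agrees otherwise |
| Randomised to placebo | day 169 | weeks 26, 36 (14 and 84 days after first dose) | no |

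**Limit against risk period, placebo-randomised children**

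- Risk period ends: 169 + 84 = day 253, or 169 + 91 = day 260.
- Last test at Visit 6 (pre-dose): limit is 169 + 112 = day 281, which is 28 or 21 days beyond the risk period. Both on-drug tests can be missed before interruption is forced.
- Last test at Visit 7, Visit 8 missed: limit is 183 + 112 = day 295, or 126 days on nintedanib with one test.
- Last test at Visit 5, Visit 6 missed: limit is 85 + 112 = day 197, or 28 days on nintedanib. The full gap therefore needs the Visit 6 test to have been done.

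**Censoring.** SAP section 5 defines last contact as the latest of several eCRF dates, including visits, concomitant treatment, drug intake and vital status. A laboratory sample is only one of them. Outside any emergency, Flow Chart footnote 6 repeats laboratory tests at follow-up only after clinically relevant changes at end of treatment, while the REP adds 28 days. Time at risk can therefore run up to 28 days past the last dose with no liver test.

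**Illustration only.** The documents give neither an event rate nor a missed-test rate. Suppose a proportion p of children have an elevation that resolves unseen if untested, and k of the 10 switchers are untested. The expected reported rate is p(10 − k)/10 among switchers and p(30 − k)/30 over all 30 children.

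| Assumed p | Switchers only, k = 2 / 5 / 10 | All 30 children, k = 2 / 5 / 10 |
|---|---|---|
| 5% | 4% / 2.5% / 0% | 4.7% / 4.2% / 3.3% |
| 10% | 8% / 5% / 0% | 9.3% / 8.3% / 6.7% |
| 20% | 16% / 10% / 0% | 18.7% / 16.7% / 13.3% |

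**The case against.** The strongest reply is that the appendix does not permit 16-week testing. It requires monitoring to be ensured, keeps the planned time as the default, includes the laboratory in home visits and adds two local routes. Sixteen weeks is where interruption becomes mandatory, and it is the same for every visit. The protocol has other safeguards too: the Safety Monitoring Committee may recommend intermediate checks in switchers (section 1.4.2), clinical symptoms of hepatic injury prompt testing (section 5.2.7.1.4), and discontinuation is to be considered if minimum procedure frequency cannot be kept (section 6.1). All of this stands. It makes a fully untested risk period a worst case that the text allows, not what the plan intends. It does not remove the mismatch, because the committee's checks are optional and the only limit with a fixed consequence is longer than the risk period.

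A reader might infer that liver tests at Visits 3 to 5 are absolutely protected, or that the rule was written for the liver. The documents support neither. The sponsor can agree to a postponement, the visit row does not mention the liver, and the 16-week laboratory limit applies there too.

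It can also be said that the words about being event free in the censoring rule leave room for a test-based reading. They may, but the SAP does not say so, and its definition of last contact points the other way.

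**Conclusion.** The point holds as an inconsistency to reconcile, together with a separate low-cost correction to the SAP. It concerns about 10 of 30 children, assuming 2:1 allocation and that all placebo children reach Visit 6. It arises only under force majeure and only if tests are missed by every available route. In that worst case the interruption limit falls 21 to 28 days after the stated risk period ends.

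Two stronger readings are tempting. The first is that the nintedanib liver rates will be too low by a known amount. The documents do not support that: the tabulated rates rest wholly on assumed p and k, the larger reductions apply to switchers only, and a persisting elevation would be found late and counted as an event with a late date. The second is that censoring at the last liver test cures the gap. It removes untested time after the last test. It leaves unchanged an untested stretch followed by a later normal result.

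**What to change.** 1. **Protocol.** Reconcile section 1.2 with the visit and laboratory rows of Table 10.9: 1 for children whose first nintedanib dose is at Visit 6. The wording must not reveal allocation, because section 4.1.5.1 keeps sites and patients blinded until after the final database lock. No interval or monitoring rule is proposed here.
2. **SAP Table 5.4.4.1: 1.** For the liver-enzyme endpoints, censor children without an event at their last liver test within the period, not at end of REP or last contact. State what happens to a child with no test in the period. Limit the change to the laboratory endpoints, because SAP section 7.8.1.3 reuses the same censoring for diarrhoea, bleeding and ILD.
3. **Local results.** Confirm that local-laboratory liver values and their upper limits of normal enter the analysis data. SAP section 5.4.4 allows for a local limit, but SAP section 7.8.2.1 speaks of central-laboratory data. Appendix 10.9 has local results sent to the investigator and asks for clinically relevant issues to be recorded as adverse events.
4. **Reporting.** Since censoring does not repair a gap followed by a normal test, report the number of children with untested gaps in their first three months on nintedanib and the length of those gaps.

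The cost is appendix wording, one SAP line, a data check and a short listing. The Kaplan-Meier curves will show slightly less follow-up.

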11. DESCRIPTION OF GLOBAL AMENDMENTS

11.1 GLOBAL AMENDMENT 1

| | | |
|--|--|---|
| Date of amendment | | 19 Jun 2020 |
| EudraCT number | | 2018-004530-14 |
| EU number | | |
| BI Trial number | | 1199-0337 (InPedILD™) |
| BI Investigational Medicinal Product(s) | | Ofev®, nintedanib |
| Title of protocol | | A double blind, randomised, placebo-controlled trial to evaluate the dose-exposure and safety of nintedanib per os on top of standard of care for 24 weeks, followed by open label treatment with nintedanib of variable duration, in children and adolescents (6 to 17 year-old) with clinically significant fibrosing Interstitial Lung Disease |
| Global Amendment due to urgent safety reasons | |  |
| Global Amendment | |  |
| Section to be changed | | 4.1.5.1 Blinding |
| Description of change | | 
“non-trial” added before “personnel from the sponsor involved in the PK analyses will be unblinded”;
 
“after the 30th patient (either nintedanib or placebo) has completed planned PK assessment in Part A” removed at the end of the statement “In order to enable early analysis of PK, selected non-trial personnel from the sponsor involved in the PK analyses will be unblinded.”;
 
“will be conducted on a continuous basis and” added into the sentence “The planned preliminary analyses will focus purely on PK (no efficacy or safety outcomes will be analysed at that time)”, and “Available PK data will be provided to the SMC for consideration when evaluating the safety of the trial.” added after the sentence;
 
“Final PK analyses and (“Fast-track”) PK/PD analyses will be reported once after availability of data from DBL 1.” removed after “No formal interim report will be generated.”;
 
“upon request” removed after “The SMC will review unblinded data”;
 
“upon request by SMC” removed after “The independent statistician of the SMC will receive the randomization code to allow the required analyses on unblinded data”.
 |

[figure not shown]
| | |
|------------------------------|---|
| Rationale for change | 
FDA recommended to conduct an interim PK evaluation at Week 2 post-dose to ensure that the systemic exposure of nintedanib with the proposed weight-based dosing regimen in patients 6 to 17 years of age is comparable to adults, so the study procedures have been updated to meet this requirement.
 
The specification “non-trial” will make clear that the personnel from the sponsor involved in the PK analyses is independent from the study team.
 |
| Section to be changed | 8.7 Administrative structure of the trial |
| Description of change | 
“members of the BI trial team and trial independent members” replaced by “external experts independent from the trial and selected BI non-trial team members”;
 
“PK and” added to the sentence “A SMC composed of ... will be established to review individual and aggregated PK and safety data at regular intervals to determine the safety profile and risk/benefit ratio and recommend dose modification, additional assessments (e.g. laboratory tests), appropriateness of further enrolment and continuation/modification/premature interruption of the study”.
 |
| Rationale for change | To clarify the independence of SMC members from trial team, and specify that the SMC will review PK data in addition to safety data. |
| Section to be changed | 1.4.2 Risks |
| Description of change | 
Added “review individual and aggregated PK and safety data at regular intervals,” “about the appropriateness of further enrolment and continuation/modification/premature interruption of the study”, and “dose modification and/or additional assessments (e.g.” to the sentence “The SMC will review individual and aggregated PK and safety data at regular intervals, advise the study team about the appropriateness of further enrolment and continuation/modification/premature interruption of the study, and might recommend dose modification and/or additional assessments (e.g. intermediate checks in those patients who switched from placebo to nintedanib at the end of the initial 24 weeks of treatment).”
 |
| Rationale for change | To specify actions expected from SMC to mitigate the risk. |

| | | |
|------------------------------|--|---|
| Section to be changed | | 4.2.2.1 Restrictions regarding concomitant treatment |
| Description of change | | Added Table 4.2.2.1: 1 Restrictions regarding use of potent P-gp and CYP3A4 inhibitors and inducers. |
| Rationale for change | | FDA recommended to exclude P-gp and CYP3A4 inducers per nintedanib prescribing information, so the restriction regarding use of potent P-gp and CYP3A4 inhibitors and inducers has been added to address the concerns raised, and minimize potential impact of these co-medications on the primary PK endpoint. |
| Section to be changed | | 3.3.3 Exclusion criteria |
| Description of change | | Added into criterion 13 the exclusion of patients with documented allergy to soya |
| Rationale for change | | The Office for Registration of Medicinal Products, Medical Devices and Biocidal Products in Poland recommended to exclude patients with documented allergy to soya per contraindications reported in the Investigator's Brochure. |
| Section to be changed | | 1.2 Drug profile, 1.3.1 Similarities and differences in the condition between populations and pharmacological rationale, 1.4.1 Benefits, 4.1.2 Selection of doses in the trial and dose modifications, 9.2 Unpublished references |
| Description of change | | Updated reference to the current Investigator's Brochure (IB) Nintedanib in Idiopathic Pulmonary Fibrosis, Systemic Sclerosis, Progressive Fibrosing Interstitial Lung Disease. |
| Rationale for change | | Updated version of the referenced documents has become available. |
| Section to be changed | | 1.2 Drug profile |
| Description of change | | Added results from the study in adults with PF-ILD. |
| Rationale for change | | Results from the study in adults with PF-ILD have become available. |
| Section to be changed | | 1.2 Drug profile, 1.3 Rationale for performing the trial, 1.4.1 Benefits, 9.1 Published references |
| Description of change | | Added references to the recently published results from the study in adults with PF-ILD. |
| Rationale for change | | Results from the study in adults with PF-ILD have become available. |
| Section to be changed | | 1.4.1 Benefits |
| Description of change | | Section updated to state that nintedanib for SSc-ILD application has been approved in Europe, US and other countries; an application for an indication for nintedanib in adults with chronic |

| | | |
|------------------------------|--|--|
| | | fibrosing interstitial lung diseases with a progressive phenotype is approved in the US and other countries, and received a positive opinion in Europe; results of the INBUILD [®] trial are available. |
| Rationale for change | | Regulatory status has changed, and results from the study in adults with PF-ILD have become available. |
| Section to be changed | | 3.1 Overall Trial Design and Plan |
| Description of change | | “Monitory” amended to “Monitoring”, and statement about implementation of a protocol amendment if additional PK data are needed replaced by detailed information about the process to be followed and PK samples to be collected if additional PK data are needed. |
| Rationale for change | | To amend a typo, and avoid a further protocol amendment. |
| Section to be changed | | 7.2.2 Primary endpoint analyses |
| Description of change | | Added details about the analysis of the primary endpoint AUC _{τ,ss} , and that further details on the PK analysis will be specified in the TSAP. |
| Rationale for change | | Clarify how PK data will be used in the primary PK analysis. |
| Section to be changed | | 7.2.7 Interim Analyses |
| Description of change | | Added information about update of primary analysis in case PK data are not sufficient and further PK data are collected. |
| Rationale for change | | Clarify that if PK data collected for the primary analysis are not sufficient, then further PK data will be collected, the primary analysis will be updated and reported in the revision of the clinical trial report based on data from DBL 2. |
| Section to be changed | | 2.1.3 Secondary endpoints |
| Description of change | | Added that the secondary endpoint “Change in height, sitting height, leg length from baseline at week 24, and week 52*” is also assessed at week 76*, and week 100*, but these time points will not be available for all patients. |
| Rationale for change | | Clarify procedures and remove inconsistency with protocol synopsis. |
| Section to be changed | | |
| Description of change | | |
| Rationale for change | | |
| Section to be changed | | |

[figure not shown]
| | | |
|------------------------------|--|--|
| Description of change | | |
| Rationale for change | | Share the information available at the time of the current amendment. |
| Section to be changed | | 5.2.7.2.2 AE reporting to the sponsor and timelines |
| Description of change | | “via fax” removed and “country specific contact details” replaced by “country specific reporting process”. |
| Rationale for change | | Adhere to changed corporate procedure and foresee submission of SAE forms by other means than fax. |
| Section to be changed | | 5.6.1 Assessment of quality of life via PedsQL™ |
| Description of change | | “and site staff” removed after “The PedsQL™ should be completed in a quiet area/room before the respondents complete any other health data forms and before they see the investigator” |
| Rationale for change | | The patient will see the site staff before completion of the questionnaire as the site staff will administer the questionnaire. |
| Section to be changed | | 5.6.6 Assessment of HRCT |
| Description of change | | “will” replaced by “might” in the sentence “In addition to confirmation of the presence of relevant fibrosis, visual and potentially quantitative analyses of the screening HRCTs might be performed to explore potential predictors of clinical outcomes”. |
| Rationale for change | | Clarify that these analyses might also not be performed, if not possible to perform. |
| Section to be changed | | 5.6.6 Assessment of HRCT |
| Description of change | | With regards to HRCTs added “screening” and specified that the same acquisition protocol specifications should be followed when possible for screening HRCTs. |
| Rationale for change | | Clarify that in some circumstances (e.g., historical HRCTs or when the devices used at a site is different from the standard referred to by the acquisition protocol) it might not be possible to follow the acquisition specifications defined by protocol. |
| Section to be changed | | 5.6.6 Assessment of HRCT, [REDACTED] |
| Description of change | | Maximum duration of storage specified for HRCT scans updated to “30 years”, [REDACTED] |

| | |
|-----------------------------|--|
| Rationale for change | Provide updated information aligned with current standard procedures for data storage. |
|-----------------------------|--|

| | |
|------------------------------|--|
| Section to be changed | Flow Chart |
| Description of change | Weeks under x visit changed from “64 plus Q12w” to “52 plus Q12w”. Days under x visit changed from “449 plus Q84d ±7” to 365 plus Q84d±7”. |
| Rationale for change | To ensure consistency with flowchart footnote 16: “Imaging follow-up will be conducted ... at 12 weeks, 24 weeks, 36 weeks, 52 weeks and every 24 weeks thereafter ... Dental examination (clinical) Follow-up will be conducted in all patients at 12 weeks, 24 weeks, 36 weeks, 52 weeks and every 24 weeks thereafter ... Dental imaging (panoramic x-ray) Follow-up will be conducted in all patients at 24 weeks, 52 weeks and every 48 weeks thereafter ...”. |
| Section to be changed | 6.2.2 Treatment period: Visits 4, 5, 6, 8, 9, X (treatment period); 6.2.3 Follow-up period and trial completion |
| Description of change | Frequency of bone imaging follow-up changed from “every 3 months, and every 6 months after the first year” to “at 12 weeks, 24 weeks, 36 weeks, 52 weeks and every 24 weeks thereafter ...”. Frequency of dental examination follow-up (clinical) changed from “every 3 months, and every 6 months after the first year” to “at 12 weeks, 24 weeks, 36 weeks, 52 weeks, and every 24 weeks thereafter ...”. Frequency of dental imaging follow-up changed from “every 6 months, and every 12 months after the first year” to “at 24 weeks, 52 weeks, and every 48 weeks thereafter ...”. |
| Rationale for change | Clarify schedule of trial procedures and ensure consistency with Flow Chart footnote. |

| | | |
|------------------------------|--|---|
| Section to be changed | | 6.2.2 Treatment period |
| Description of change | | “A scheduled visit (V3-Vx)” replaced by “The first visit after the EoT visit” as subject of the sentence “will be skipped if the EoT visit occurs within 4 weeks prior to the scheduled visit.” |
| Rationale for change | | Clarify trial procedures and ensure consistency within Flow Chart footnote (**). |
| Section to be changed | | Flow Chart footnote 16, 5.2.5 Assessment of pathological findings of epiphyseal growth plate, 5.2.6 Assessment of pathological findings on dental examination or imaging, 6.2.2 Treatment period |
| Description of change | | “who qualified for randomisation” added after “will be conducted in all patients” for MRI/x-ray, dental examination, and dental imaging. |
| Rationale for change | | Specify that these procedures will only be done if patient qualified for randomization, to avoid unnecessary procedures. |
| Section to be changed | | 6.2.2 Treatment period: Visit 2 (baseline) |
| Description of change | | About the conduct of MRI/x-ray, dental examination, dental imaging at Visit 2, replaced “immediately before or after” with “immediately after” in the sentence “If it’s not possible to conduct this procedure on the day of the visit, the procedure can be done in the weeks immediately after the visit”. At the end of the sentence added a reference to the HRCT acquisition protocol available in the ISF for details. |
| Rationale for change | | Amend the information as these procedures should not be done before Visit 2, and refer the investigator to the Image Acquisition Guideline for details. |
| Section to be changed | | 6.2.2 Treatment period: Visits 4, 5, 6, 8, 9, X (treatment period); 6.2.3 Follow-up period and trial completion |
| Description of change | | About the conduct of MRI/x-ray, dental examination, dental imaging at Visits 4, 5, 6, 8, 9, X and in patients who prematurely discontinued trial medication, at the end of the sentence “If it’s not possible to conduct this procedure on the day of the visit, the procedure can be done in the weeks immediately after the visit” added a reference to the HRCT acquisition protocol available in the ISF for details. |
| Rationale for change | | Refer the investigator to the Image Acquisition Guideline for details. |

| | | |
|------------------------------|--|---|
| Section to be changed | | Title page |
| Description of change | | Trial acronym added in brackets after the BI Trial No. |
| Rationale for change | | Specify trial acronym. |
| Section to be changed | | 8.7 Administrative structure of the trial |
| Description of change | | Purpose of the Disease Review Committee (DRC) amended from “To determine what percent of screen patients met protocol criteria for inclusion” to “To determine how well the protocol inclusion criteria were able to identify the intended population”. Word “for” added to “... central reading for all patients evaluated for study participation at Visit 1”. |
| Rationale for change | | Amend incorrect information ensuring consistency with the DRC Charter, and clarify the following sentence. |
| Section to be changed | | 8.3.1 Source documents |
| Description of change | | Missing words and commas added to the following sentences: “Copies of source documents necessary for the purposes of the trial will be provided to the relevant committee/vendor, as listed below: to the Disease Review Committee for retrospective evaluation of patients’ characteristics compared to protocol inclusion criteria, to the Adjudication Committee for the adjudication of defined events, to the Safety Monitoring Committee for the evaluation of possible efficacy signals and for monitoring of safety throughout the conduct of the study, to the external radiology expert for central reading of HRCTs, to the external pathology expert for central reading of biopsies, to the external radiology expert for central reading of bone MRIs/x-rays, to the external paediatric dentistry expert for central reading of panoramic x-rays.” |

[figure not shown]
| | | |
|------------------------------|--|--|
| Rationale for change | | Add text which was missing due to a technical issue. |
| Section to be changed | | 6.2.1 screening |
| Description of change | | Removed “)” |
| Rationale for change | | Typo |

11.2 GLOBAL AMENDMENT 2

| | | |
|--|--|--|
| Date of amendment | | 14 Jun 2021 |
| EudraCT number EU number | | 2018-004530-14 |
| BI Trial number | | 1199-0337 (InPedILD™) |
| BI Investigational Medicinal Product(s) | | Ofev®, nintedanib |
| Title of protocol | | A double blind, randomised, placebo-controlled trial to evaluate the dose-exposure and safety of nintedanib per os on top of standard of care for 24 weeks, followed by open label treatment with nintedanib of variable duration, in children and adolescents (6 to 17 year-old) with clinically significant fibrosing Interstitial Lung Disease |
| Global Amendment due to urgent safety reasons | |  |
| Global Amendment | |  |
| Section to be changed | | Flow Chart, Flow Chart footnote 12, 6.1 Visit Schedule, 6.2.2 Treatment period |
